## 4.2 Prohibited Medications and Restrictions

Use of and changes in concomitant medications will be recorded in the subject's source documents and the electronic data capture (EDC) system. All prescription drugs, herbal products, vitamins, minerals, and over-the-counter medications are to be recorded.

Any concomitant medication with the exception of those listed below may be given at the discretion of the investigator. However, the investigator has the responsibility of ensuring that details regarding the concomitant medication are recorded for the subject in the EDC system. Complete information is expected for any medication prescribed during the trial.

The prescribing information for all medications, including Trogarzo® should be reviewed carefully. The guidance provided in the respective contraindications, warning, and precautions section for any medication must be followed to prevent any potentially serious or life-threatening drug interactions. Refer to the current Trogarzo® Package Insert and/or Investigator Brochure and/or Product Monograph for relevant information.

The following medications are not to be administered concomitantly in HIV-infected individuals:

- Any vaccines other than influenza or COVID vaccine during the 7 days before Day 1/Baseline through EOS;
- All investigational drugs from 30 days before Day 1/Baseline through EOS, with the exception of investigational components of a qualifying stable ART regimen

In HIV-uninfected subjects vaccines may be administered during the course of the study with approval by the study staff; however, no investigational drugs may be administered.

## 4.3 Safety Monitoring and Toxicity Management Plan

### Sentinel Group

This trial will employ a sentinel group of 5 subjects to determine the safety of progressively shortening the administration time while increasing the drug concentration of Trogarzo® with the goal of delivering an 800 mg dose (5.32 mL at 150 mg/mL) via IV push over 30 seconds.

A dose-limiting toxicity (DLT) will be defined as:

- Any Grade 3 or greater toxicity that the study investigators recognize as probably or definitely attributable to Trogarzo® administration. Grade 3 and 4 laboratory abnormalities must be confirmed by a repeat test obtained as soon as possible following the initial result

OR

- Any subject with Grade 2 infusion-related reaction and/or cytokine release syndrome (see [Appendix B – DAIDS Grading Table V2.1](#) for cytokine release syndrome).

**The first 2 subjects in the Sentinel Group will be enrolled and treated at least 2 weeks prior to the enrollment and treatment of the remaining 3 subjects.**

If no DLT occurs within 7 days of Trogarzo® shortened IV infusion, bolus, or push administration then dosing of additional subjects may continue with approval of the DMC.

If 1 DLT occurs within 7 days of Trogarzo® dosing at a shortened IV infusion, bolus, or push administration then the DMC should be notified; however, dosing may continue. The individual experiencing the DLT should resume dosing as per current FDA-approved administration instructions and the subject will discontinue from the study.

If 2 DLTs occur within 7 days of Trogarzo® dosing at a shortened IV infusion, bolus, or push administration then such administration should be suspended and further dosing of Trogarzo® should resume as per current FDA-approved administration instructions.

Any SAE deemed related to the change in administration time and concentration of Trogarzo® in any participant in the Sentinel Group will result in cessation of dosing at increased concentration and over intervals <15 minutes. The DMC should review the event and all scheduled Trogarzo® dosing should resume as per current FDA-approved administration instructions to avoid loss of virologic control. The DMC may recommend resumption of the Sentinel Group dosing schedule after review of the SAE.

### **Core Group**

Once the Sentinel group has completed Day 99 and the DMC has reviewed the safety data and approved additional enrolment and treatment with Trogarzo® given as an IV push over 30 seconds, the Core Group may begin enrolment and dosing as per the study design.

The Core Group will consist of 15 subjects who will receive an 800 mg maintenance dose of Trogarzo® in accordance with the prescribing information (diluted in normal saline and administered over 15 minutes via IVI) at Day 1/Baseline and again at Day 15. Every 2 weeks thereafter through

Day 71 (10 weeks), maintenance doses will be administered via undiluted IV push over 30 seconds. At Day 85 (12 weeks), HIV-infected Core Group subjects will revert to diluted IVI dosing over 15 minutes in accordance with the Trogarzo® prescribing information. HIV-uninfected Core Group subjects will discontinue dosing after the Day 71 study drug administration.

As above, a DLT will be defined as any Grade 3 or greater toxicity that the study investigators recognize as probably or definitely attributable to Trogarzo® administration. Grade 3 and 4 laboratory abnormalities must be confirmed by a repeat test obtained as soon as possible following the initial result.

In the absence of the occurrence of DLTs, the DMC should formally review all safety data at the following timepoints:

1. After 5 subjects in the Core Group receive 2 doses of Trogarzo® IV push (IVP) over 30 seconds.
2. After the first 5 subjects in the Core Group receive 4 doses of Trogarzo® IV push over 30 seconds and the second 5 subjects receive 2 doses of Trogarzo® IVP over 30 seconds.
3. At the conclusion of the study of all 15 Core Group subjects.

**For HIV-uninfected healthy volunteers:**

If 1 DLT occurs within 7 days of a subject receiving Trogarzo® by IVI or IV push over 30 seconds, then the DMC should be notified, and dosing of additional Core Group subjects may continue. However, the individual experiencing the DLT should discontinue dosing and be observed for 28 days prior to study discontinuation.

If 2 DLTs occur within 7 days of a subject receiving Trogarzo® by IVI or by IV push over 30 seconds, then the DMC should be notified; however, dosing of additional HIV-1 infected Core Group subjects may continue. The individuals experiencing the DLT should discontinue dosing and be observed for 28 days prior to study discontinuation. The DMC should at this point review.

If 3 DLTs occur within 7 days of a subject receiving Trogarzo® by IVI or IV push over 30 seconds, then the DMC should be notified, and further dosing of Core Group subjects should be suspended. All Core Group subjects should resume dosing as per current FDA-approved administration instructions.

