**For HIV-1 infected individuals:**

If 1 DLT occurs within 7 days of a subject receiving Trogarzo® IV push over 30 seconds, then the DMC should be notified, and dosing of additional Core Group subjects may continue. However,

the individual experiencing the DLT should resume dosing as per current FDA-approved administration instructions and the subject will discontinue from the study.

If 2 DLTs occur within 7 days of a subject receiving Trogarzo® IV push over 30 seconds, then the DMC should be notified; however, dosing of additional Core Group subjects may continue. The individuals experiencing the DLT should resume dosing as per current FDA-approved administration instructions and the subjects will discontinue from the study.

If 3 DLTs occur within 7 days of a subject receiving Trogarzo® IV push over 30 seconds, then the DMC should be notified, and further dosing of Core Group subjects should be suspended. All Core Group subjects should resume dosing as per current FDA-approved administration instructions.

Any SAE deemed related to study drug administration will result in cessation of dosing by IV push over 30 seconds. The DMC should review the event and all Trogarzo® dosing should resume as per current FDA-approved administration instructions to avoid loss of virologic control. The DMC will determine whether dosing by IV push over 30 seconds may resume in additional participants.

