**For HIV-uninfected healthy volunteers:**

If 1 DLT occurs within 7 days of a subject receiving Trogarzo® by IVI or IM injection, then the DMC should be notified, and dosing of additional IM Group subjects may continue. However, the individual experiencing the DLT should discontinue dosing and be observed for 28 days prior to study discontinuation.

If 2 DLTs occur within 7 days of a subject receiving Trogarzo® by IVI or by IM injection then the DMC should be notified; however, dosing of additional HIV-1 uninfected IM Group subjects may continue. The individuals experiencing the DLT should discontinue dosing and be observed for 28 days prior to study discontinuation. The DMC should at this point review.

If 3 DLTs occur within 7 days of a subject receiving Trogarzo® by IVI or by IM injection, then the DMC should be notified, and further dosing of IM Group subjects should be suspended. All IM Group subjects should resume dosing as per current FDA-approved administration instructions.

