**For HIV-infected individuals:**

If 1 DLT occurs within 7 days of a subject receiving Trogarzo® via IM injection, then the DMC should be notified, and dosing of additional IM Group subjects may continue. However, the individual experiencing the DLT should resume dosing as per current FDA-approved administration instructions and the subject will discontinue from the study.

If 2 DLTs occur within 14 days of a subject receiving Trogarzo® via IM injection, then the DMC should be notified; however, dosing of additional IM Group subjects may continue. The individuals experiencing the DLT should resume dosing as per current FDA-approved administration instructions and the subjects will discontinue from the study.

If 3 DLTs occur within 14 days of a subject receiving Trogarzo® via IM injection, then the DMC should be notified, and further dosing of IM Group subjects should be suspended. All IM Group subjects should resume dosing as per current FDA-approved administration instructions.

Any SAE deemed related to study drug administration will result in cessation of dosing via IM injection. The DMC should review the event and all Trogarzo® dosing should resume as per current FDA-approved administration instructions to avoid loss of virologic control. The DMC will determine whether dosing by IM injection may resume in additional participants.

Refer to [Appendix C](#) for further information on the management of suspected anaphylactoid reactions. Study drug should only be administered in a setting that allows for rapid access to emergency cardiopulmonary support services in the event of a life-threatening infusion-related AE (e.g., anaphylaxis).

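### A laboratory DLT found at a scheduled draw cannot meet the 7-day DLT rules, because safety labs are drawn about 14 days after each dose

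*Protocol*

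**What the plan says.** **Definition (Protocol 4.3).** A DLT is "Any Grade 3 or greater toxicity that the study investigators recognize as probably or definitely attributable to Trogarzo® administration". Laboratory events are expressly included: "Grade 3 and 4 laboratory abnormalities must be confirmed by a repeat test obtained as soon as possible following the initial result". The Sentinel, Core and IM parts each give this definition, and none sets a time limit.

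**Count rules (Protocol 4.3).**
- Sentinel: DLTs count "within 7 days of Trogarzo® dosing at a shortened IV infusion, bolus, or push administration" or in equivalent 7-day wording.
- Core volunteers: "If 1 DLT occurs within 7 days of a subject receiving Trogarzo® by IVI or IV push over 30 seconds", with the same window for two and three DLTs. After a first DLT, "the individual experiencing the DLT should discontinue dosing and be observed for 28 days prior to study discontinuation".
- HIV-infected Core: "If 1 DLT occurs within 7 days of a subject receiving Trogarzo® IV push over 30 seconds, then the DMC should be notified", again 7 days throughout.
- IM volunteers: "If 1 DLT occurs within 7 days of a subject receiving Trogarzo® by IVI or IM injection, then the DMC should be notified", again 7 days throughout.
- HIV-infected IM: 7 days for the first DLT, then a longer window for the second and third: "If 2 DLTs occur within 14 days of a subject receiving Trogarzo® via IM injection, then the DMC should be notified".

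**Stopping rules (Protocol 4.4).** Two Core volunteer DLTs within 7 days stop volunteer enrolment. The other DLT stops (two in Sentinel, three in Core push or IM) have no window, but the DMC must attribute the events to a faster rate, a higher concentration, or both.

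**Laboratory timing.** The Synopsis and Tables 1 to 4 place hematology and chemistry every 2 weeks at dosing visits. Section 6.2 describes the visits between pushes as non-laboratory. Listing 16.2.8.1 of the IM SAP and Listing 16.2.7.1.1 of the IV push SAP state that labs are assessed before dosing. Protocol 7.2.1 asks for Grade 3 or 4 results to be repeated within 72 hours of the site learning of them.

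**The concern.** The definition admits an event that most of the action rules cannot recognise when it is found at a scheduled draw. The sample that would reveal a laboratory toxicity of one dose is taken just before the next dose, after the 7-day window has closed. The Protocol also does not say whether a laboratory DLT is dated by its first sample or by the confirming repeat, or to which dose it belongs.

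At stake are consequences that are meant to follow without discretion: taking the affected subject off the experimental schedule, counting the event toward suspension, and stopping volunteer enrolment. Healthy volunteers matter most here. They have no HIV to treat, and their rules also cover standard infusions, including a 2000 mg load.

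**Working it through.** The plan gives no figure to reproduce. The check counts the rules and then measures the gap from each counted dose to the next scheduled draw.

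**1. Rules in 4.3 by window**

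| Group | Rules | 7-day | 14-day |
|---|---|---|---|
| Sentinel (0, 1, 2 DLTs) | 3 | 3 | 0 |
| Core volunteers (1, 2, 3) | 3 | 3 | 0 |
| Core HIV-infected (1, 2, 3) | 3 | 3 | 0 |
| IM volunteers (1, 2, 3) | 3 | 3 | 0 |
| IM HIV-infected (1, 2, 3) | 3 | 1 | 2 |
| Total | 15 | 13 | 2 |

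Without the Sentinel no-DLT rule the count is 12 of 14.

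**2. Counted doses and the next scheduled hematology/chemistry draw (Tables 1 to 4)**

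| Schedule | Counted doses (day) | Next draw (day) | Gap ≤7 days |
|---|---|---|---|
| Sentinel | 29, 43, 57, 71, 85 | 43, 57, 71, 85, 99 | 0 of 5 |
| HIV-infected Core | 29, 43, 57, 71 | 43, 57, 71, 85 | 0 of 4 |
| HIV-infected IM | 29, 43, 57, 71 | 43, 57, 71, 85 | 0 of 4 |
| Volunteers, Core or IM | -55, -41, -27, -13, 1, 15, 29, 43, 57, 71 | -41, -27, -13, 1, 15, 29, 43, 57, 71, 85 | 0 of 10 |

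Every nominal gap is 14 days. With a shift of a days at the dose visit and b at the draw, each from -1 to +1, the gap is 14 + b - a, so 12 to 16 days. The minimum of 12 exceeds 7.

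Section 6.2 conflicts with Table 2: it puts volunteers' labs before Day 1 at every 4 weeks from Day -55. On that text the draws are Days -55, -27 and 1, and the gaps after Days -55 and -27 are -27 - (-55) = 28 and 1 - (-27) = 28 days.

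CD4 counts are left out. Table 3 as extracted appears to show one at Day 36, but its columns look shifted.

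**3. The two 14-day rules.** A nominal 14-day gap just meets them, so they catch the scheduled draw, including Day 85 after the last injection (71 + 14 = 85). A gap of 15 or 16 days would miss.

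**4. Volunteers' standard infusions.** Days -55, -41, -27, -13, 1 and 15 make 6 of 10 doses. They are given at the approved rate and dilution or, for the load, over 60 minutes, so the window-free 4.4 stops do not reach them. Only 7-day DLT rules apply.

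**5. Sensitivity: dating by the repeat.** If a result takes T days to reach the site, the repeat is due by day T + 3 after the sample. The sample day is usually also a dose day, so the repeat falls within 7 days of that next dose if T ≤ 4; at T = 5 a repeat using the full 72 hours falls on day 8. Turnaround is not stated. Assuming T ≤ 4, the event would count after 4 of 5, 3 of 4, 3 of 4 and 9 of 10 doses in the order of the table, but against the dose after the sample. A Day 29 pre-dose result could then be charged to the first push, injection or shortened infusion.

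**The case against.** A 7-day window is a sensible choice for acute reactions to a new rate or route of an approved dose, and Protocol 1.2 reports no laboratory changes of clinical concern in the earlier SC/IM study. The other safeguards are also substantial.

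- **Awareness.** Under 8.8 the DMC discusses abnormal laboratory results and receives all Grade 3 and 4 AEs. Under 7.2.1 the investigator should discuss Grade 3 or 4 results with the medical monitor or sponsor. Section 6.6 allows unscheduled visits, and a draw at one of these could fall within 7 days. A reader might infer that laboratory DLTs would go unseen; the documents do not support that.
- **Last push or injection.** A reader might also infer that a laboratory DLT after the final experimental dose escapes every stopping decision. It largely does not. The window-free 4.4 stops apply, on the reasonable view that undiluted IM counts as increased concentration. Core screening waits for Sentinel Day 99 and DMC approval. The 14-day rules cover HIV-infected IM subjects at the nominal gap.

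Both points stand and narrow the concern. They do not remove it, because awareness is not a prespecified action. The withdrawal route in 7.2.1 and the best-interest ground in 5.3.1 are discretionary. The drug-related AE ground in 5.3.1 is limited to administration and the observation period. The related-laboratory discontinuation line in IM SAP Table 14.1.2 is a reporting category. Nor does an acute-reaction rationale explain why confirmed laboratory abnormalities are in the definition.

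**Conclusion.** The conflict is real and should be corrected. Dated by its initial sample, a laboratory DLT found at a scheduled draw meets none of the 13 seven-day rules in 4.3 and does not meet the 4.4 Core volunteer enrolment stop; only an unscheduled draw could. The practical gap has three parts:

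1. the automatic individual discontinuation in 4.3;
2. the DLT rules for volunteers' six standard infusions;
3. the two-DLT Core volunteer enrolment stop.

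A stronger reading would be that the plan charges laboratory events to the wrong route. That needs dating by the confirming repeat. The Protocol leaves dating open, but 8.3 records an onset date for each AE, and the SAP listings place pre-dose labs in the preceding period. That SAP convention governs reporting, not DLT counting, yet both points favour the initial sample. The counts in step 5 also rest on an assumed turnaround, so they show an ambiguity to close, not an expected error.

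The conclusion assumes the scheduled visits and windows as written. The documents give no rate for related Grade 3 or 4 laboratory events, so the number of missed events cannot be estimated.

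**What to change.** Keep the existing windows for clinical events. Add to the 4.3 count rules and the 4.4 volunteer rule:

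*A confirmed Grade 3/4 laboratory DLT is dated by its initial sample and attributed to the most recent preceding dose; it counts if found at any draw up to and including the first scheduled draw after that dose (including its visit window).*

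For volunteers' last dose on Day 71 this means the Day 85 draw. Extending to Day 99 (99 - 71 = 28 days after the dose) is optional. The wording also keeps a Day 29 pre-dose result from being charged to the first experimental dose. State at the same time whether Table 2 or the 4-weekly text in 6.2 governs volunteers' labs before Day 1, since that fixes the first scheduled draw.

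The cost is a protocol amendment with IRB approval (Protocol 11.3). A few more laboratory events may count toward the rules, and three volunteer DLTs suspend Core dosing, so that is a real change to a stopping rule. No visits or blood draws are added.

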**For HIV-1 infected individuals:**

If 1 DLT occurs within 7 days of a subject receiving Trogarzo® IV push over 30 seconds, then the DMC should be notified, and dosing of additional Core Group subjects may continue. However,

the individual experiencing the DLT should resume dosing as per current FDA-approved administration instructions and the subject will discontinue from the study.

If 2 DLTs occur within 7 days of a subject receiving Trogarzo® IV push over 30 seconds, then the DMC should be notified; however, dosing of additional Core Group subjects may continue. The individuals experiencing the DLT should resume dosing as per current FDA-approved administration instructions and the subjects will discontinue from the study.

If 3 DLTs occur within 7 days of a subject receiving Trogarzo® IV push over 30 seconds, then the DMC should be notified, and further dosing of Core Group subjects should be suspended. All Core Group subjects should resume dosing as per current FDA-approved administration instructions.

Any SAE deemed related to study drug administration will result in cessation of dosing by IV push over 30 seconds. The DMC should review the event and all Trogarzo® dosing should resume as per current FDA-approved administration instructions to avoid loss of virologic control. The DMC will determine whether dosing by IV push over 30 seconds may resume in additional participants.

**For HIV-uninfected healthy volunteers:**

If 1 DLT occurs within 7 days of a subject receiving Trogarzo® by IVI or IM injection, then the DMC should be notified, and dosing of additional IM Group subjects may continue. However, the individual experiencing the DLT should discontinue dosing and be observed for 28 days prior to study discontinuation.

If 2 DLTs occur within 7 days of a subject receiving Trogarzo® by IVI or by IM injection then the DMC should be notified; however, dosing of additional HIV-1 uninfected IM Group subjects may continue. The individuals experiencing the DLT should discontinue dosing and be observed for 28 days prior to study discontinuation. The DMC should at this point review.

If 3 DLTs occur within 7 days of a subject receiving Trogarzo® by IVI or by IM injection, then the DMC should be notified, and further dosing of IM Group subjects should be suspended. All IM Group subjects should resume dosing as per current FDA-approved administration instructions.

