## SYNOPSIS

Protocol Number:	TMB-302
Title:	A Phase 3 Study of the Safety of Trogarzo® Administered as an Undiluted “IV Push” over a Reduced Interval or as an Intramuscular Injection in Clinically Stable HIV-1 Infected Trogarzo® Experienced Patients and Healthy HIV-uninfected Volunteers
Sponsor:	TaiMed Biologics, USA Corp. [name]
Study Phase:	3
Subjects and Investigator Sites:	A total of approximately 40 subjects will be enrolled into this study. Approximately twenty (20) will receive Trogarzo® as an intravenous (IV) push and approximately 20 subjects will receive Trogarzo® as an intramuscular (IM) injection at approximately 7-8 sites in the United States. Subjects who receive Trogarzo® as an IV Push can also receive Trogarzo® as an IM injection once they complete the IV push portion of study. After 20 subjects enroll to complete the IV push portion of the study, subjects who enroll may participate in the IM portion exclusively.
Study Drug Dosage and Route of Administration:	The study drug, Trogarzo®, is a humanized IgG4 monoclonal antibody (MAb) approved for use in treatment-experienced subjects in combination with other antiretroviral agents for the treatment of multi-drug resistant HIV-1 infection and is administered via intravenous infusion (IV).  Maintenance doses of 800 mg Trogarzo® will be administered to all study subjects every 2 weeks throughout their participation in the study.  For subjects receiving Trogarzo® as an IV push, the Day1/Baseline and Day 15 doses will be administered as diluted intravenous infusions (IVI - 800 mg in 250 mL normal saline; 3.2 mg/mL) over 15 minutes in accordance with Trogarzo® prescribing information. Subsequent Trogarzo® doses on study will be administered at increased concentration over a shorter interval (<15 minutes – see Study Design for more detail).  For subjects receiving Trogarzo® via IM injection, the Day 1/Baseline and Day 15 doses will be administered as diluted IVI over 15 minutes in accordance with Trogarzo® prescribing information. The subsequent four (4) Trogarzo® doses on study will be administered as an IM injection.

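### At the third DLT, the volunteer rules in Protocol 4.3 suspend dosing and then tell all subjects to resume approved infusion, a route the trigger itself counts

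*Protocol*

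**What the plan says.** Section 4.3 (Safety Monitoring and Toxicity Management Plan) gives each of the Core and IM Groups two sets of DLT rules, one for HIV-infected subjects and one headed "For HIV-uninfected healthy volunteers".

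In the IM Group, the last step of the volunteer rule begins "If 3 DLTs occur within 7 days of a subject receiving Trogarzo® by IVI or by IM injection". The DMC is then notified and "further dosing of IM Group subjects should be suspended". The sentence after that says "All IM Group subjects should resume dosing as per current FDA-approved administration instructions".

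The Core Group volunteer rule is built the same way. Its trigger counts infusion and 30-second push, and it closes with "All Core Group subjects should resume dosing as per current FDA-approved administration instructions".

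At the lower steps of both volunteer rules, the affected people stop. At two DLTs the text is "The individuals experiencing the DLT should discontinue dosing and be observed for 28 days prior to study discontinuation".

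The Synopsis describes the drug as "approved for use in treatment-experienced subjects in combination with other antiretroviral agents for the treatment of multi-drug resistant HIV-1 infection", and Section 3.3 identifies the approved regimen as a diluted 15-minute infusion.

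**The concern.** The third-DLT step is the strongest protection these rules give volunteers. As written, it suspends dosing and then directs everyone in the group to resume by the approved method, which is infusion. Since the same step counts DLTs after infusion, some or all of the three events may have come from that route. Site staff who follow the text literally would give further infusions to healthy people immediately after the trigger meant to protect them. These people have no therapeutic need for the drug and fall outside its approved indication. The sentence also covers *all* subjects, whereas the steps just above it tell volunteers with a DLT to stop.

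**Working it through.** No arithmetic settles this point, and the plan gives no figure to reproduce. The check is a comparison of texts.

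**1. The rules in Section 4.3 that return subjects to approved administration after a set number of DLTs**

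| Rule | DLTs needed | Routes counted | What is suspended | Is approved infusion among the routes counted? |
|---|---|---|---|---|
| Sentinel | 2 | shortened infusion, bolus, push | that type of administration | No |
| Core, HIV-infected | 3 | push | further dosing of Core subjects | No |
| IM, HIV-infected | 3 | IM | further dosing of IM subjects | No |
| Core, uninfected | 3 | infusion or push | further dosing of Core subjects | **Yes** |
| IM, uninfected | 3 | infusion or IM | further dosing of IM subjects | **Yes** |

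In the first three rows the sequence makes sense: the experimental route is stopped and subjects go back to a route that did not trigger the rule. In the two volunteer rows the route returned to is one of the routes counted.

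**2. How much of volunteer dosing is infusion.** Section 3.1 schedules infusions on Days -55, -41, -27, -13, 1 and 15, which is 6 doses. Push or IM doses follow on Days 29, 43, 57 and 71, which is 4 doses. So 6 of 10 scheduled doses (60%) are infusions. For a volunteer still in the infusion phase when the third DLT occurs, resuming approved infusion restores what that person was already receiving, and the suspension has no effect.

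**3. The order of the steps.** At one DLT the affected volunteer stops. At two, the affected volunteers stop and the DMC reviews; the Core Group text at that step expressly lets only HIV-infected subjects continue. At three, all resume. For a Core volunteer without a DLT, the third step is therefore more permissive than the second.

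**4. The reason given for resuming.** Section 4.3 states a reason only in the related-SAE rules, where it is to prevent loss of virologic control. That cannot apply to someone without HIV.

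**5. The rest of the protocol.** Elsewhere the two populations are kept apart. HIV-infected subjects go back to infusion at the end of the experimental doses, while volunteers stop after Day 71 (Sections 3.1, 4.1, 6.2 and 6.3). The Synopsis limits the return to routine infusion to HIV-infected subjects. Section 4.5 has volunteers treated with research-labelled drug supplied by the sponsor.

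**6. Whether Section 4.4 resolves it.** Its three-DLT rule covers only events the DMC attributes to a faster rate or higher concentration, so DLTs after standard infusion fall outside it. Its one rule that counts infusion concerns two DLTs in Core Group volunteers. That rule ends volunteer enrollment and lets those already enrolled who have not met the DLT criteria finish. Neither rule says what happens to volunteers at the third DLT.

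**The case against.** The best defence is that *suspended* and *resume* refer to different things. The Sentinel rule says explicitly that the experimental form of administration is suspended and standard infusion resumes; on this view the volunteer rules are a shortened version. This explains the HIV-infected rules well. It does not rescue the volunteer rules, because their trigger is not confined to the experimental route and their text suspends dosing of subjects rather than a route.

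Second, *approved administration instructions* can fairly be read as dilution and rate rather than indication. Every volunteer dose in this trial lies outside the approved indication by design. That is right, so the lack of an approved use does not by itself prove the sentence wrong. It is accurate but secondary.

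Third, by the third event the first two affected volunteers have already been told to stop, so the sentence mainly concerns unaffected volunteers. Section 4.4 elsewhere accepts that unaffected volunteers may continue. This narrows the consequence, but *all* still makes no exception for those who had a DLT, and the Section 4.4 provision stops at two DLTs and the Core Group.

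Fourth, the DMC is notified at every step, reviews at the second, and may recommend changes under Section 8.8. That makes an unexamined return to infusion less likely. However, the instruction to resume is not made conditional on any DMC review.

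Finally, the sentence may have been carried over from the HIV-infected rules, or meant for HIV-infected members only. Either is plausible, but the text sits under the volunteer heading and does not say so.

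**Conclusion.** The concern holds. In both volunteer rules the third-DLT step counts events after infusion, suspends dosing, and then returns every subject in the group to infusion with no exception for volunteers. It is best described as an internal inconsistency in a safety rule.

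The instruction applies to each uninfected volunteer still on dosing in the affected group at the third DLT. Section 4.3 plans 15 Core and about 20 IM subjects, and the documents do not give the number of volunteers, so those totals are only upper limits. The fault matters only if three DLTs occur, each of Grade 3 or higher and judged probably or definitely attributable to the drug. The documents give no basis for estimating how likely that is. The conclusion rests on reading the sentence as written, under the heading where it stands. It should be corrected, but it does not affect the trial's analyses.

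**What to change.** The sponsor should reconcile the suspend and resume sentences in the third-DLT step of both volunteer rules in Section 4.3 (Core and IM). The revised text should:

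- state separately what happens to HIV-infected subjects and to uninfected volunteers after three DLTs;
- say whether the suspension covers all dosing or only the experimental route, given that DLTs after infusion are counted;
- say how the step applies to volunteers who themselves had a DLT, so that it agrees with the one- and two-DLT steps;
- agree with Section 4.4 and with the end of volunteer dosing after Day 71.

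Which clinical rule to adopt is for the sponsor and the DMC, and none is proposed here. The cost is protocol wording, with the IRB approval that Section 11.3 requires for an amendment. Sample size, assessments and the SAP are unaffected.
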